7.3 Analysis Sets

The following analysis sets will be used in the statistical analyses.

Full Analysis Set (FAS): The FAS will consist of all patients who received investigational study drug.

Modified Full Analysis Set (mFAS): The mFAS will consist of all patients in the FAS but will exclude data points

Per-Protocol Analysis Set: The Per-Protocol Analysis Set will consist of all patients in the FAS who received ABP-450 within the study dose range of 150 to 350 units but will exclude all patients who had significant protocol violations or do not receive more than one treatment of ABP-450 within the OLE study.

Safety Analysis Set (SAS): The SAS will consist of all patients who received investigational study drug.

Safety Analysis Set with Retreatment (SASR): The SASR will consist of all patients in the SAS but will exclude patients who do not receive more than one treatment of ABP-450 within the OLE study.

7.4 Description of Subgroups to be Analyzed

No subgroup analyses are planned.

7.5 Statistical Analysis Methodology

Variables

will generally be summarized using number of observations, mean, standard deviation, median, minimum, maximum, and missing data (for continuous variables) and using frequencies, percentages, and missing data (for categorical variables). Data will be listed in data listings.

Details of the statistical analyses, methods, and data conventions will be described in the SAP.

7.5.1 Analysis of Primary Estimand

The proportion of patients with treatment-related SAEs up to Week 52 will be summarized for the SASR.

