6.2.1.2 Serious Adverse Events

An SAE is defined as any event that

- results in death
- is immediately life-threatening
- requires inpatient hospitalization or prolongation of existing hospitalization
- results in persistent or significant disability/incapacity
- is a congenital anomaly/birth defect

Adverse events will be assessed from the time the patient signs the ICF until exit from the study (ie, 52 weeks or end of treatment [ET] after Day 0 "rollover").

Serious AEs that occur more than 56 days (ie, 8 weeks) after the last dose of investigational study drug and the patient has exited the study need not be reported unless the investigator considers them related to investigational study drug.

At every study visit, patients will be asked a standard non-leading question to elicit any medically related changes in their well-being. They will also be asked if they have been hospitalized, had any accidents, used any new medications, or changed concomitant medication regimens (both prescription and over-the-counter medications).

In addition to patient observations, AEs identified from any study data (eg, laboratory values, physical examination findings, changes in 12-lead ECG results) or identified from review of other documents that are relevant to patient safety will be documented on the AE page in the eCRF.

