3.4. Dose Adjustment/Modifications

Patients were enrolled in the ABP-19002 OLE study with the opportunity to either maintain the original Phase 2 dose or modify the dose at the investigator's discretion. As the blind will not be broken, the placebo patients (who were entered into one of the dose groups in the ABP-19000

study) can be administered any dose between 150 and 350 units of ABP-450, based on the investigator's discretion and clinical judgment. Retreatments are also based on investigator's discretion and clinical judgment.

4. General Statistical Considerations

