4.5.3. Safety Analysis Set (SAF)

The SAF will consist of all patients who received at least one dose of the investigational study drug. The SAF will be used to tabulate all safety data excluding the primary estimand.

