4.5.4. Safety Analysis Set with Retreatment (SAFR)

The SAFR will consist of all patients in the SAF but will exclude patients who do not receive more than one treatment of ABP-450 within the OLE study. The SAFR will be used for analysis of the primary estimand.

5. Patient Disposition

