5.1. Disposition

Patient disposition will be summarized by overall treatment group and presented in a listing for patients in the Enrolled Set. The disposition of patients will include the number and percentage of patients for the following categories:

- Patients enrolled.
- Patients included in the mFAS.
- Patients included in the SAF.
- Patients included in the SAFR.
- Patients who discontinued treatment with corresponding reasons for treatment discontinuation.
- Patient included in the SAF with corresponding reasons for treatment discontinuation.
- Patients who withdrew from the study with corresponding reasons for study withdrawal.

The reasons for discontinuation of ABP-450 treatment or withdrawal from the study include:

• Adverse Event

- Death
- Lack of Efficacy
- Lost to Follow-up
- Non-Compliance with Study Drug
- Physician Decision
- Pregnancy
- Study Terminated by Sponsor
- Withdrawal by Subject
- Other

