8.1.7. Adverse Events Leading to Treatment Discontinuation

Incidence of TEAEs with a study drug action taken as "Drug Withdrawn" will be summarized by SOC and PT by treatment group within each treatment cycle as described in Section 8.1. At each level of patient summarization, a patient is counted once if the patient reported one or more events. Percentages will be calculated out of the number of patients in the SAF.

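### The primary related-SAE proportion counts only patients given more than one OLE injection, so a related SAE after the first injection that prevents retreatment cannot enter it.

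*Protocol*

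**What the plan says.** Protocol 7.5.1 fixes the primary analysis: "The proportion of patients with treatment-related SAEs up to Week 52 will be summarized for the SASR". Protocol 7.3 defines the set: "The SASR will consist of all patients in the SAS but will exclude patients who do not receive more than one treatment of ABP-450", counting treatments within the OLE only. SAP 4.5.4 repeats the definition under the abbreviation SAFR and adds: "The SAFR will be used for analysis of the primary estimand". SAP 4.5.3 draws the same line from the other side: "The SAF will be used to tabulate all safety data excluding the primary estimand". The two documents agree, so this is a deliberate rule.

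Three other places bear on who receives a second injection:

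- SAP 5.1 includes adverse event and death in the list that begins "The reasons for discontinuation of ABP-450 treatment or withdrawal from the study include".
- SAP 8.1.7 plans a table of "Incidence of TEAEs with a study drug action taken as" drug withdrawn.
- SAP 3.4 says: "Retreatments are also based on investigator's discretion and clinical judgment".

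Protocol 6.2.1.2 counts as serious any event that "results in death".

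**The concern.** Membership of the primary set is settled after treatment has begun, by an event (the second injection) that the outcome itself can prevent. A patient who has a related SAE after OLE injection 1 and is not injected again disappears from the primary proportion altogether. The plan expects adverse events and deaths to stop treatment and leaves retreatment to the investigator's judgment, so the link between outcome and membership is foreseeable.

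This is the primary result of a study whose primary objective is safety. It could read 0% although related SAEs had occurred after the first OLE injection, and a reader of the headline figure would not know that patients had been selected in this way.

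**Working it through.** **Inputs from the documents.** About 60 patients (protocol 7.2) or 59 (SAP 4.3); set membership requires at least two OLE injections (protocol 7.3, SAP 4.5.4); follow-up is 52 weeks. The documents give no expected SAE rate, retreatment rate or count of single-injection patients, so there is no planned figure to reproduce. All rates below are assumptions.

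**Formula.** Let p be the proportion of all treated patients with a related SAE, r1 the share of those patients who receive a second OLE injection, and r0 the same share among the others. Then

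SASR proportion = p·r1 / (p·r1 + (1 − p)·r0).

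This is below p only if r1 < r0, equals p if r1 = r0, and exceeds p if r1 > r0. Patients whose related SAE followed a later injection were retreated by definition, so r1 falls below 1 only through first-injection events that were not followed by retreatment.

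| Assumed p | Assumed r0 | r1 = 0 | r1 = 0.5 | r1 = 1 |
|---|---|---|---|---|
| 5% | 0.95 | 0% | 0.025/0.9275 = 2.7% | 0.05/0.9525 = 5.2% |
| 5% | 0.80 | 0% | 0.025/0.785 = 3.2% | 0.05/0.81 = 6.2% |
| 2% | 0.95 | 0% | 0.01/0.941 = 1.1% | 0.02/0.951 = 2.1% |

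**Whole-patient examples.** 60 treated, with three patients without a related SAE not retreated; Clopper-Pearson 95% intervals in brackets.

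- One related SAE, after injection 1. All treated: 1/60 = 1.7% (0.0 to 8.9). SASR: 0/56 = 0% (0 to 6.4) if that patient is not retreated, 1/57 = 1.8% (0.0 to 9.4) if retreated.
- Three related SAEs, all after injection 1. All treated: 3/60 = 5.0% (1.0 to 13.9). SASR: 0/54 = 0% (0 to 6.6) if none is retreated, 1/55 = 1.8% (0.0 to 9.7) if one, 2/56 = 3.6% (0.4 to 12.3) if two, 3/57 = 5.3% (1.1 to 14.6) if all three.
- Three related SAEs, one after injection 1 without retreatment and two after later injections. All treated 3/60 = 5.0%; SASR 2/56 = 3.6%.

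**Sensitivity.** In the second example, changing the number of other patients not retreated to 0, 6 or 12 leaves the SASR figure at 0% (0/57, 0/51, 0/45) when none of the three is retreated. When all three are retreated it gives 3/60 = 5.0%, 3/54 = 5.6% and 3/48 = 6.3%. With 59 patients, 3/59 = 5.1% compares with 0/53 = 0%, 1/54 = 1.9%, 2/55 = 3.6% and 3/56 = 5.4%.

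**Could the case arise?** With an assumed per-patient risk of 2%, the chance of at least one related SAE among 60 patients is 1 − 0.98^60 = 70%; it is 45% at 1% and 95% at 5%.

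**The case against.** The strongest defence is the objective: the study is about repeat injections. Because the ABP-19000 blind stays unbroken, a patient's first OLE injection may be the first ABP-450 that patient has received in the programme. Requiring two OLE treatments guarantees repeat exposure. This explains the set but does not justify it. The set does not isolate risk after repeat exposure: a related SAE after OLE injection 1 counts if the patient is later retreated and drops out if it is the reason for not retreating. Patients given active drug in ABP-19000 are already on a repeat dose at OLE injection 1, yet they lose their treatment-ending events too.

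Several other points stand and limit the finding:

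- The events are kept elsewhere in the SAF: related TEAEs (SAP 8.1.4), treatment-emergent SAEs (8.1.6), drug withdrawals (8.1.7) and the deaths listing (8.1.11). With about 60 patients they would be noticed. Among the sections that can be read, however, none is described as giving the related-SAE proportion in all treated patients.
- SAP 4.1 bases safety analyses on the SAF and protocol 4.2.2 promises to use data from early discontinuations. Neither is strictly breached, since SAP 4.1 allows analyses on other populations and the SAF tables use the data. The primary figure is an exception to both, not a contradiction.
- The primary estimand wording, SAP 8.1.1 and the item list of SAP 8.1.2 cannot be read in the public text. An all-treated related-SAE count may already be planned there. That would not change the set that protocol 7.5.1 and SAP 4.5.3 and 4.5.4 name for the primary figure.
- The analysis is descriptive, no decision threshold is visible, and the illustrated intervals overlap.

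**Conclusion.** The concern holds: the primary set is wrong as written. By definition, a related SAE after the first OLE injection that prevents retreatment contributes nothing to the primary proportion, however many such patients there are.

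The direction rests on one assumption, that patients with a related SAE are retreated less often than others. That is plausible, since such an event is a natural reason not to inject again, but the documents do not quantify it. If retreatment is equally frequent in both groups there is no understatement. In the illustrations a true 5.0% is reported as anything from 0% to 5.3%. No event is lost from the report as a whole. The defect lies in which set supplies the headline safety figure, and it should be corrected.

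**What to change.** In protocol 7.5.1 and SAP 4.5.3 and 4.5.4, and in SAP 8.1.1 where it names the set, make the related-SAE proportion in the SAS/SAF (at least one OLE dose) the primary figure. Report the SASR/SAFR proportion beside it, labelled as conditional on having been retreated, so that the repeat-exposure question is still answered. Check the estimand wording in protocol 2.2.2 and 7.1 and SAP 3.2.1 so that its population matches. If SAP 8.1.2 already holds the all-treated related-SAE count, only designation and labelling need to change.

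The cost is wording in both documents, with the IRB/IEC submission that protocol 11.2.1 requires for an amendment, and at most one extra table. No new data are needed. The headline figure may be less favourable, and the all-treated set mixes former placebo patients' first exposures with repeat exposures; showing both sets side by side deals with the latter.

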7.5.2 Analysis of Secondary Estimands

The analysis of the first secondary efficacy estimand is based on a regression model with change

7.5.3 Other Analyses

Summary statistical analyses will be provided for demographics, background characteristics, medical history, and physical examination.

7.5.4 Interim Analyses

No interim analyses are planned.

8 Data Quality Assurance

The sponsor or its designee will perform the quality assurance and quality control activities of this OLE study, including regular monitoring visits to study sites and meeting with site personnel. However, the investigator generating the data will be responsible for the accuracy, completeness, and reliability of the study data presented to the sponsor.

8.1 Data Management

As part of the responsibilities assumed by participating in the study, the investigator agrees to maintain adequate case histories for the patients treated as part of the research under this protocol. The investigator agrees to maintain accurate eCRFs and source documentation as part of the case histories. These source documents may include laboratory reports

All eCRF information is to be filled in. If an item is not available or is not applicable, this fact should be indicated. Blank spaces should not be present unless otherwise directed. A correction to source documentation should be made by striking through the incorrect entry with a single line and the corrected information should be entered adjacent to the deleted item. The correction must be initialed and dated by the person making the correction.

Investigative site personnel will enter patient data into an electronic data capture system. The analysis data sets will be a combination of these data and data from other sources (eg, laboratory data).

Clinical data management will be performed in accordance with applicable Aeon Biopharma, Inc. standards and data cleaning procedures to ensure the integrity of the data (eg, removing errors and inconsistencies in the data). Adverse event terms will be coded using MedDRA, an internal validated medical dictionary, and concomitant medications will be coded using the World Health Organization Drug Dictionary.

9 Ethics

9.1 Independent Ethics Committee or Institutional Review Board

Federal regulations and the ICH guidelines require that approval be obtained from an IRB/IEC before participation of human patients in research studies. Before study onset, the protocol, informed consent, advertisements to be used for the recruitment of study patients, and any other written information regarding this study to be provided to the patient must be approved by the IRB/IEC. Documentation of all IRB/IEC approvals and of the IRB/IEC compliance with ICH guideline E6 (R2): Good Clinical Practice (GCP) will be maintained by the site and will be available for review by the sponsor or its designee.

All IRB/IEC approvals should be signed by the IRB/IEC chairman or designee and must identify the IRB/IEC name and address, the clinical protocol by title or protocol number or both, and the date of approval or a favorable opinion was granted.

The investigator is responsible for providing written summaries of the progress and status of the study at intervals not exceeding 1 year or otherwise specified by the IRB/IEC. The investigator must promptly supply the sponsor or its designee, the IRB/IEC, and where applicable, the institution, with written reports on any changes significantly affecting the conduct of the study or increasing the risk to patients.

9.2 Ethical Conduct of the Study

The study will be performed in accordance with the ethical principles that have their origin in the Declaration of Helsinki, ICH GCP, the protocol, and all applicable regulations.

9.3 Patient Information and Consent

A written informed consent in compliance with United States Title 21 Code of Federal Regulations (CFR) Part 50 shall be obtained from each patient before entering the study or performing any study procedure. An informed consent template may be provided by the sponsor to investigative sites. If any institution-specific modifications to study-related procedures are proposed or made by the site, the consent should be reviewed by the sponsor or its designee or both before IRB/IEC submission. Once reviewed, the consent will be submitted by the investigator to his or her IRB/IEC for review and approval before the start of the study. If the ICF is revised during the course of the study, all active participating patients must sign the revised form.

Before recruitment and enrollment, each prospective patient will be given a full explanation of the study and be allowed to read the approved ICF. Once the investigator is assured that

the patient understands the implications of participating in the study, the patient will be asked to give consent to participate in the study by signing the ICF.

The investigator shall retain the signed original ICF(s) and give a copy of the signed original form to the patient.

10 Investigator's Obligations

The following administrative items are meant to guide the investigator in the conduct of the study but may be subject to change based on industry and government standard operating procedures, working practice documents, or guidelines. Administrative changes will be reported to the IRB/IEC but will not result in protocol amendments.

10.1 Confidentiality

All laboratory specimens, evaluation forms, reports, and other records will be identified in a manner designed to maintain patient confidentiality. All records will be kept in a secure storage area with limited access. Clinical information will not be released without the written permission of the patient, except as necessary for monitoring and auditing by the sponsor, its designee, the FDA, or the IRB/IEC.

The investigator and all employees and coworkers involved with this study may not disclose or use for any purpose other than performance of the study any data, record, or other unpublished, confidential information disclosed to those individuals for the purpose of the study. Prior written agreement from the sponsor or its designee must be obtained for the disclosure of any said confidential information to other parties.

10.2 Financial Disclosure and Obligations

Investigators are required to provide financial disclosure information to allow the sponsor to submit the complete and accurate certification or disclosure statements required under 21 CFR 54. In addition, the investigator must provide to the sponsor a commitment to promptly update this information if any relevant changes occur during the course of the investigation and for 1 year following the completion of the study.

Neither the sponsor **mattern** is financially responsible for further testing or treatment of any medical condition that may be detected during the Screening process. In addition, in the absence of specific arrangements, neither the sponsor **mattern** is financially responsible for further treatment of the patient's disease.

10.3 Investigator Documentation

Prior to beginning the study, the investigator will be asked to comply with ICH E6 (R2) 8.2 and Title 21 of the CFR by providing the following essential documents, including but not limited to:

• IRB/IEC approval

- Original investigator-signed investigator agreement page of the protocol
- Form FDA 1572, fully executed, and all updates on a new fully executed Form FDA 1572 (applicable to study sites in the United States only)
- Curriculum vitae for the investigator and each subinvestigator listed on Form FDA 1572 (applicable to study sites in the United States only)
- Financial disclosure information to allow the sponsor to submit complete and accurate certification or disclosure statements required under 21 CFR 54. In addition, the investigators must provide to the sponsor a commitment to promptly update this information if any relevant changes occur during the course of the investigation and for 1 year after the completion of the study
- IRB/IEC-approved informed consent, samples of site advertisements for recruitment for this study, and any other written information regarding this study that is to be provided to the patient
- Laboratory certifications and normal ranges for any local laboratories used by the site, in accordance with 42 CFR 493

10.4 Study Conduct

The investigator agrees that the study will be conducted according to the principles of ICH E6 (R2). The investigator will conduct all aspects of this study in accordance with all national, state, and local laws or regulations. Study information from this protocol will be posted on publicly available clinical trial registers before enrollment of patients begins.

10.5 Adherence to Protocol

The investigator agrees to conduct the study as outlined in this protocol in accordance with ICH E6 (R2) and all applicable guidelines and regulations.

10.6 Adverse Events and Study Report Requirements

By participating in this study, the investigator agrees to submit reports of SAEs to the sponsor and/or IRB/IEC according to the timeline and method outlined in the protocol. In addition, the investigator agrees to submit annual reports to the study site IRB/IEC as appropriate.

10.7 Investigator's Final Report

Upon completion of the study, the investigator, where applicable, should inform the institution; the investigator/institution should provide the IRB/IEC with a summary of the study's outcome and the sponsor and regulatory authorities with any reports required.

10.8 Records Retention

Essential documents should be retained until at least 2 years after the last approval of a marketing application in an ICH region and until there are no pending or contemplated marketing applications in an ICH region or at least 2 years have elapsed since the formal discontinuation of clinical development of the investigational study drug. These documents should be retained for a longer period, however, if required by the applicable regulatory requirements or by an agreement with the sponsor. It is the responsibility of the sponsor to inform the investigator/institution as to when these documents no longer need to be retained.

10.9 Publications

After completion of the study, the data may be considered for reporting at a scientific meeting or for publication in a scientific journal. In these cases, the sponsor will be responsible for these activities and will work with the investigators to determine how the manuscript is written and edited, the number and order of authors, the publication to which it will be submitted, and other related issues. The sponsor has final approval authority over all such issues.

Data are the property of the sponsor and cannot be published without prior authorization from the sponsor, but data and publication thereof will not be unduly withheld.

11 Study Management

The administrative structure will include a scientific steering committee and event adjudication committee.

The scientific steering committee, composed of key opinion leaders expert in the treatment of patients with cervical dystonia, will consult with the sponsor on the design of the study protocol, review the data, and analyze the data incorporated into the final study report.

